Targeting Worry to Improve Sleep

NCT03684057

June 5, 2019

Procedures:

Individuals will be recruited primarily via online advertising (e.g. Facebook and Google AdWords). Those who learn about the study via social media will be prompted to complete an online screening questionnaire. Those who learn about the study via other means (e.g. flyers, word of mouth) will review the questions from the online screener during the initial screening phone call. After the screening call, eligible participants will be scheduled for their baseline visit at the Brown Mindfulness Center ([name]). Study staff will send potential participants a copy of the consent form to review prior to the baseline visit. Participants will be asked to complete four study visits in total: three visits will be in-person and one will be completed online.

At the baseline visit, potential participants will be asked to review the consent form, ask any questions they may have about the study and if they decide to participate in the study, they will be asked to sign the consent form. Study participants will be given a copy of the signed consent form for their records.

Randomization Plan: A research team member who is not involved with the study will prepare sealed envelopes with an individual's group assignment using a block randomization scheme designed by an independent statistician. After the consent process and prior to administration of assessments, study participants will be randomized into one of two groups: 1) Group A – the treatment as usual group; 2) Group B - the UA intervention group. The participant will be given a sealed envelope and asked to open it to determine their group assignment.

Based on the participant's group assignment, the research team member will pull up the appropriate survey in Qualtrics and ask the participant to complete the first portion of the baseline assessment. After they have concluded, they will be instructed on how to complete the shape-matching task and then left alone to complete it on the study laptop while the researcher keeps track of the time from outside.

Upon completion of the assessments, the participant will be instructed to download either the Fitbit app (Group A) or Unwinding Anxiety and the Fitbit app (Group B). Please see below for onboarding specific to group assignment.

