If the participant is randomized to Group A - They will be given a Fitbit Inspire to track the quality of their sleep and asked to download the Fitbit app to their smartphone. They will be provided with the information necessary to set up their account and instructed how to use the app to track their sleep. Please refer to the included script, *Fitbit Setup Guide* attachment, for more details. They will be asked to wear the Fitbit and record what time they went to bed & woke up in a sleep diary (which will be provided) for one week after the baseline visit, one week before the 3rd visit (in-person), and one week before the 4th visit (in-person). The total number of hours slept per night will be collected for the post-baseline period in Qualtrics via a personalized survey link while data will be collected in person for the other two use periods and recorded in Qualtrics. Upon completion of the third assessment, the UA app will be downloaded to his/her smartphone at no cost and with lifetime access. The participant will be instructed to watch the first module of the app and will review its features with the research team member to ensure they do not have any questions (see *UA Setup Guide* attachment for more details).

If the participant is randomized to Group B - They will be given a Fitbit and the process outlined above will be followed. In addition, the UA app will be downloaded to his/her smartphone and the same process will be followed as outlined above.

Both groups are expected to complete the following tasks / assessments at each research visit:

Baseline – In-person

- Group A will complete the first eight items using a personalized survey link (based on participant ID) via Qualtrics

- Group B will complete the first seven items using a personalized survey link via Qualtrics and the seventh, the GAD-7, will be completed as part of the Unwinding Anxiety assessment.
- Both groups will complete the shape matching task on a study laptop.
 1. Demographics. This form will be filled out in Qualtrics (age, gender, socioeconomic status, employment, education, race/ethnicity, relationship status) (approximately 3 minutes)

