 2. Five Facet Mindfulness Questionnaire (FFMQ) non-reactivity scale. The non-reactivity scale is a subscale of the 39-item FFMQ which is a self-report psychological measure of mindfulness skills. This subscale contains 7 items which are presented on a 6-point Likert scale ranging from 1 (almost always) to 6 (almost never). This questionnaire is included in the protocol. (approximately 1 minute)
 3. Penn State Worry Questionnaire (PSWQ). The PSWQ is a 16-item self-report measure of worry with items presented on a 5-point Likert scale ranging from 1 (not at all typical of me) to 5 (very typical of me). This questionnaire is included in the protocol. (approximately 3 minutes)
 4. Multidimensional Assessment of Interoceptive Awareness (MAIA). The MAIA is a 32-item self-report questionnaire comprised of 8 subscales including: noticing, not-distracting, not-worrying, attention regulation, emotional awareness, self-regulation, body listening, and trusting. Items are rated on a 6-point Likert scale ranging from 0 (never) to 5 (always). This questionnaire is included in the protocol. (approximately 5 minutes)
 5. PROMIS Sleep & Anxiety items. The PROMIS Sleep & Anxiety includes 5 questions taken from the PROMIS v1.0 Sleep Disturbance questionnaire which focus on the interaction between worry and sleep. This questionnaire is included in the protocol. (approximately 1 minute)
 6. Worry Interfering with Sleep scale (WIS). The WIS is a single item self-report question that asks individuals to rate what percent of time worry interfered with their ability to get to or stay asleep. This questionnaire is included in the protocol. (approximately 1 minute).
 7. Expectancy. These three questions assess treatment usefulness, confidence, and likelihood to recommend on a 9-point Likert scale from 1 (Not at all confident or Not at all useful) to 9 (Very confident or Very useful) and from 0 to 100%. This questionnaire is included in the protocol (approximately 1 minute).
 8. Generalized Anxiety Disorder 7-items (GAD-7). The GAD-7 is a 7-item measure of anxiety rated on a 4-point Likert scale ranging from 0 (Not at all sure) to 3 (Nearly every day). This questionnaire is included in the protocol. (approximately 2 minutes)

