Analyses will be conducted in R using an intent-to-treat approach (ITT). Fischer's exact tests for categorical and Kruskal Wallis tests for continuous variables will be used to determine any between-group differences in baseline demographics. To examine between-group differences in behavioral outcome measures at the primary endpoint (2 months), Welch's t-tests will be used along with Mann Whitney U tests for data that violates the assumption of normality. A series of Generalized Estimating Equations (GEE) will be used to estimate the adjusted intervention effect by regressing change in outcomes at each follow-up on time, group, time*group and confounders identified a priori (using correlation analysis. GEE's are used for longitudinal data in order to account for within-subject covariance over time. False Discovery Rate will be used to correct for multiple comparisons.

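### The GEE covariates are to be chosen by correlation analysis, and nothing keeps out variables rated after the arm is known, such as expectancy

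*Combined protocol and SAP*

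**What the plan says.** The first paragraph of the Statistical Analysis Plan specifies two analyses of the behavioural outcomes. One is an unadjusted comparison at the 2-month primary endpoint (Welch's t-test, or Mann-Whitney where normality fails). The other is a GEE for the adjusted effect, "regressing change in outcomes at each follow-up on time, group, time*group and confounders identified a priori". The rule for choosing covariates is "confounders identified a priori (using correlation analysis"; the parenthesis is never closed, and no covariate, candidate set or cut-off follows. Section 7 (Analysis) says that all analyses are done once data collection is complete.

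The Randomization Plan sets the order of the baseline visit:
- "After the consent process and prior to administration of assessments, study participants will be randomized into one of two groups".
- The participant then learns the arm by opening an envelope.
- Only after that does the survey start: "Based on the participant's group assignment, the research team member will pull up the appropriate survey in Qualtrics"; the baseline questionnaires follow.

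Item 7 of the baseline list is Expectancy: "These three questions assess treatment usefulness, confidence, and likelihood to recommend on a 9-point Likert scale". Both arms complete it: "Group A will complete the first eight items using a personalized survey link", and "Group B will complete the first seven items using a personalized survey link via Qualtrics and the seventh, the GAD-7". (The list numbers the GAD-7 as item 8. That slip does not alter the point.)

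Nothing in the Statistical Analysis Plan restricts covariates to variables fixed before allocation, and nothing mentions expectancy.

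**The concern.** A covariate set chosen from correlations in the trial's own data is not a priori. In a randomised comparison any baseline imbalance in pre-allocation variables is due to chance, so there is no systematic confounding for such a screen to find. Pre-allocation covariates are useful for precision, and for that they can be named now.

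The more serious part is the open candidate set. A variable measured after the participant knows the arm can itself be changed by allocation. If it also correlates with the outcome, the screen will tend to select it, partly because the intervention works. Adjusting for it then shifts the group coefficient, and the model no longer estimates the effect of assignment. The adjusted and unadjusted 2-month results could disagree for that reason alone, and the covariate set could differ from outcome to outcome.

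**Working it through.** **The plan's own figure.** The only numerical design figure is 80 enrolled for 64 complete data sets (section 4). 64/80 = 0.80, so a 20% loss is implied. No alpha, power, effect size, SD or allocation ratio is given, so the 64 cannot be derived and the plan offers no effect size to test against. The point does not rest on it. Every effect size below is an assumption.

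**Size of the shift.** Let G be the arm (1 = app), E expectancy in SD units and Y the outcome in SD units, scored so that higher is better. Let d be the arm difference in E, b the within-arm slope of Y on E, and τ the total effect of assignment:

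- E = d·G + u
- Y = τ·G + b·u + e

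Putting u = E − d·G into the second line gives Y = (τ − d·b)·G + b·E + e. With E in the model, the group coefficient is therefore τ − d·b instead of τ. This holds whether expectancy is a mediator or only a prognostic marker that assignment has moved.

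With τ = 0.50:

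| d | b | τ − d·b |
|---|---|---|
| 0 | any | 0.50 |
| 0.5 | 0.1 | 0.45 |
| 0.5 | 0.2 | 0.40 |
| 1.0 | 0.1 | 0.40 |
| 1.0 | 0.2 | 0.30 |

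**Adding the screen.** Simulated trials with 32 per arm, a Pearson screen of E against Y at p < 0.05 (an assumed cut-off), and E in the linear model only when selected. For d = 0.5-1.0 and b = 0.1-0.2:

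- Expectancy is selected in 22-62% of trials.
- When it is selected, the mean adjusted effect is 0.30-0.43 SD.
- Over all trials the mean is about 0.32-0.48 SD. A repeat with 40,000 trials per scenario gave 0.33-0.47, so the last digit is simulation noise.
- Power over all trials falls from about 50% to 24-45%.
- With d = 0.2, the mean over all trials is 0.465-0.492 SD and power is 46-49%. With d = 0, the mean stays at 0.49-0.50 SD.

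**A second set of assumptions.** τ = 0.70 SD is about what 32 per arm detects with 80% power at two-sided 5%, if allocation is 1:1. For d = 0.3-0.8 and within-arm correlation 0.1-0.5, the coefficient with expectancy in the model runs from 0.70 − 0.3×0.1 = 0.67 to 0.70 − 0.8×0.5 = 0.30, so 4% to 57% is removed. In the middle case (d = 0.5, r = 0.3) it is 0.70 − 0.15 = 0.55. A large-sample GEE with exchangeable correlation, three follow-ups and time-by-group terms gave 0.70 without expectancy and 0.53 with it, so the result is not peculiar to a single-time linear model. With no true effect, the same middle case gives a mean estimate after screening of −0.12 SD and a rejection rate of 7.8% against a nominal 5%.

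**Screening alone.** With 12-22 true pre-allocation covariates screened on the outcome at p < 0.05, 0.10 or 0.20 and N = 64-80, type I error stayed at 4.3-5.7%.

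**Collinearity.** With equal arms, the variance inflation from E is 1 + d²/4: 1.06 at d = 0.5 and 1.25 at d = 1.0. Standard errors rise by √1.06 to √1.25, about 3% to 12%.

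**The case against.** The strongest reply is that the harm is hypothetical. Expectancy is nowhere named as a candidate. The plan speaks of confounders, and the only baseline set that it names is demographics, so a careful analyst might never enter expectancy. This stands as a limit on the claim: the fault is an open rule, not a stated intention.

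A reader might also infer that expectancy rates the treatment just assigned, and so must differ by arm. The documents do not support that. The item says only treatment, and Group A receives the same app after its third assessment, so both arms may be rating the app and the difference may be small. What remains is that the rating is given after the arm is known, so allocation can affect it.

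A third reply is that correlation analysis may mean correlations from other data, or ones examined before the outcome models. The resulting list is still missing, and section 7 places all analyses after data collection.

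The direction is also assumed. The shift is toward zero only if expectancy is higher in the app arm and predicts improvement; with opposite signs the effect is inflated.

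**Conclusion.** The point holds as a fault in specification with a possible, conditional bias. The plan labels the GEE covariates a priori but gives a data-driven rule for choosing them, and that rule can admit a variable that allocation has changed. If expectancy is selected and differs by arm, the adjusted effect is off by the product of the arm difference and the within-arm slope: anything from nothing to about 0.20 SD out of 0.50 (1.0 × 0.2) in the main scenarios. These rest wholly on assumed values, because the documents give none.

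Three stronger conclusions are not supported:
- That the 2-month primary-endpoint test is biased. The Welch or Mann-Whitney comparison uses no covariates and is unaffected.
- That screening by correlation in itself inflates false positives. With true pre-allocation covariates, type I error stayed near 5%.
- That expectancy would be seriously collinear with group. A variance inflation of 1.06-1.25 is modest.

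The correction should be made before the data are examined, but the trial's unadjusted result does not depend on it.

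**What to change.** Delete the parenthetical about correlation analysis and state one short covariate list, the same for every outcome and fixed before any data are examined. Limit it to variables that allocation cannot affect, for example demographics, and the screening PSWQ and WIS if these are retained. Retention needs checking: section 5 deletes the online record once a person agrees to take part, but keeps screening forms for eligible participants. Scores from the baseline visit are not an equivalent substitute, because they too are self-reported after the envelope is opened.

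Add that expectancy will not enter the intent-to-treat effect models, and will be reported by arm or used in exploratory analyses only.

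The cost is a sentence or two in the Statistical Analysis Plan and no extra data collection. The price is giving up the data-driven choice of further covariates.

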3. $\geq 5/10$ on Worry Interfering with Sleep scale (WIS)
4. Able to read and speak English, because the Unwinding Anxiety app is available in English only.
5. Owns a smartphone (UA app can only be used on a smartphone)
6. Willingness to wear the Fitbit Inspire tracker

Exclusion:

1. If using psychotropic medication - not on a stable dosage for at least 6 weeks
2. Medical disorder of the severity that would interfere with ability to participate (e.g. cancer, multiple sclerosis, Parkinson's disease, ALS, etc. These disorders impact sleep quality which could confound study outcomes.)
3. As needed (i.e. prn) benzodiazepine or hypnotic sleep aid
4. Known sleep disorder (e.g. obstructive sleep apnea, restless leg syndrome – because these disorders impact sleep quality.)
5. Psychotic disorder (Mindfulness meditation has to be carefully monitored with people experiencing psychosis. We are not able to provide this type of monitoring given budget constraints.)
6. Post-Traumatic Stress Disorder (Mindfulness meditation has to be carefully monitored with people experiencing PTSD. We are not able to provide this type of monitoring given budget constraints.)
7. Severe Depression (PHQ-2 score > 3) (People experiencing severe depression may also experience sleep disorders which could confound study outcomes.)
8. Current shift work employment (People working alternate shifts may have sleep quality problems which could confound study outcomes.)
9. BMI > 30. (People who are obese may have sleep quality problems which could confound study outcomes.)
10. Evening caffeine use (Caffeine use late in the day can impact the quality of a person's sleep, hence the possibility of confounding study outcomes.)
11. Pregnancy (Women in various stages of pregnancy often have sleep quality problems, hence the possibility of confounding study outcomes.)
12. New parents whose child is not sleeping through the night (New parents are often awakened every 3 – 4 hours by a newborn which could confound study outcomes)
13. Lives in same household as someone already enrolled in this study (To prevent study participants from sharing study information with one another.)

Participant enrollment target:

Our goal is to collect 64 complete and usable data sets, so our plan is recruit and enroll 80 participants.

Enrolling 80 participants will be sufficient to cover any participants who don't complete the study and it will allow us to meet our N of 64.

Check-ins

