Sleep period time (SPT) will be calculated from the paper sleep diaries (PSDs) by subtracting self-reported bedtime from wake time. Fitbit recorded bedtime, wake time, number of sleep minutes, and number of awake minutes will be used to calculate estimated TST and sleep efficiency (SE). To improve reliability, average estimated TST will only be calculated for participants with ≥ 3 days recorded during each wear period. Analysis will utilize the same approach as described for the behavioral measures with the addition of a complete case (CC) approach; participants who did not complete the baseline wear period will be excluded from analysis. For the ITT analysis, we will compare the robustness of our findings using two statistical approaches for handling missing data. First, we will use inverse probability weighting with propensity scores. This is a two-step method: 1) using logistic regression, the probability of missingness is modeled as a function of baseline covariates and baseline values of the outcome and 2) the inverse of the propensity scores (predicted probabilities of dropout from the first step) serve as weights in our regression model of the outcomes. Provided the data is missing at random (MAR) or that the probability of missingness can be fully explained by observable data, this approach produces asymptotically unbiased estimates. To allow for the possibility that the MAR assumption may not hold, we will also use a second approach, pattern mixture models, in which the distribution of the outcome is assumed to follow a mixture of two distributions: one for those who complete follow up and another for those who do not. We will subsequently examine effects under a per-protocol analysis.

Mediation analyses will be conducted using both the Baron and Kenny four-step approach in addition to causal mediation models. In the causal mediation analysis, we will focus on the natural direct and indirect effects and use the bootstrap method with 1,000 bootstrapped resamples to compute the standard errors and 95% confidence interval.

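### The SAP names no variance estimator or reference distribution for its GEE models; with 64 to 80 participants the usual uncorrected sandwich would make the adjusted results modestly anti-conservative, and a small-sample correction is a cheap improvement

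*Combined protocol and SAP*

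**What the plan says.** The Statistical Analysis Plan section obtains the adjusted effect by "regressing change in outcomes at each follow-up on time, group, time*group and confounders identified a priori". Its only remark on inference from these models is that "GEE's are used for longitudinal data in order to account for within-subject covariance over time". No working correlation, variance estimator, small-sample correction, degrees of freedom or reference distribution is given. The covariates are "confounders identified a priori (using correlation analysis", with no list or count. FDR correction follows, without a procedure, level or family.

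For sleep outcomes the SAP carries over the same approach. For missing data it adds inverse-probability weights that "serve as weights in our regression model of the outcomes", and supports that method by a large-sample argument only. The one variance method it does name is the bootstrap, for causal mediation.

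The between-group comparison at the 2-month primary endpoint is a separate step that uses Welch's t-test or the Mann-Whitney test.

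On size, section 4 (Participant Population, enrollment target) states: "Our goal is to collect 64 complete and usable data sets, so our plan is recruit and enroll 80 participants".

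**The concern.** The ordinary GEE sandwich variance is built from fitted residuals. These are smaller than the true errors, so the variance is biased downward when the number of clusters is limited. Here the clusters are participants. The bias grows with each participant-level covariate. A normal reference also ignores the sampling variability of the estimated variance, which matters most far out in the tails.

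Both effects make intervals too narrow and p-values too small. A multiplicity procedure whose early steps compare p-values with thresholds well below 5% works in the region where the proportional error is greater. At stake are the adjusted intervention effect, the time-by-group results, and possibly the FDR control.

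**Working it through.** **Inputs from the documents**
- Clusters: 64 complete data sets, 80 enrolled (section 4).
- Follow-ups: "Participants will be asked to complete four study visits in total" (Procedures); taking off baseline leaves 3.
- Mean model: time, group and time-by-group. With time categorical (assumed) this is 3 + 3 = 6 parameters before any covariate.

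**Assumptions, because the documents are silent**
- 1:1 allocation. The Randomization Plan says only "using a block randomization scheme designed by an independent statistician".
- Within-person correlation 0.5 and independence working correlation.
- 0 to 8 covariates.
- Benjamini-Hochberg at 5% with 6 to 16 outcomes.
- Uncorrected sandwich with normal critical values as the usual form of GEE.

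**The plan's own figure.** 64 / (1 − 0.20) = 80, so the enrolment target reproduces if 20% loss is allowed. That 20% is implied by 64/80, not stated. The 64 itself cannot be derived, because no alpha, power, effect size or SD is given.

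**Simulation under the null.** 20,000 replicates per setting; the contrast is the group effect at 2 months.

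| Setting | Estimated / true SE | Type I error at nominal 5% |
|---|---|---|
| N=64, 0 covariates | 0.987 | 6.0% |
| N=64, 3 covariates | 0.971 | 6.3% |
| N=64, 5 covariates | 0.951 | 6.9% |
| N=64, 8 covariates | 0.939 | 7.3% |
| N=80, 5 covariates | 0.959 | 6.3% |
| N=80, about 20% dropout, weighted, 5 covariates | 0.942 | 7.3% |
| N=80, about 20% dropout, weighted, 8 covariates | 0.919 | 7.7% |

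A separate run of 12,000 replicates per setting gave 5.7% for N=80 with no covariates. This is the lower end of the unweighted range.

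**Why relative inflation grows.** Take the SE ratio 0.951 (N=64, 5 covariates) and compute 2 × [1 − Φ(0.951 × z)]:
- Nominal 5%: 0.951 × 1.960 = 1.864, giving 6.2% (×1.25).
- Nominal 0.05/6 = 0.83%: 0.951 × 2.638 = 2.509, giving 1.21% (×1.45).
- Nominal 0.05/16 = 0.31%: 0.951 × 2.955 = 2.810, giving 0.49% (×1.58).

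That is the bias alone. The simulation also includes the variability of the SE and gives 6.9% (×1.37), 1.56% (×1.87) and 0.65% (×2.08). The absolute excess moves the other way: 6.85 − 5.00 = 1.85 percentage points, 1.56 − 0.83 = 0.73, and 0.65 − 0.31 = 0.34. At an illustrative 0.05/13 = 0.38% (13 tests is an assumption), another simulation gave 0.48 to 0.75%.

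**Realised FDR.** Global null, unweighted, 6,000 replicates, nominal 5%, Monte Carlo SE 0.28 points. The uncorrected method gave:
- 7.1% (N=80, 3 covariates, 6 outcomes);
- about 8.3% (N=64, 5 covariates, 6 outcomes);
- 8.5 to 10.2% (N=64, 5 covariates, 16 outcomes);
- 10.0% (N=64, 8 covariates, 16 outcomes).

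**With the correction.** A Kauermann-Carroll-type variance with t gave:
- SE ratio 0.99 to 1.00;
- type I error 5.0 to 5.2% at 5%, 0.78 to 0.97% at 0.83%, and 0.28 to 0.42% at 0.31%;
- realised FDR 4.6 to 5.1%.

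Mancl-DeRouen with t gave 3.6 to 4.8% at nominal 5%.

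**The case against.** The strongest reply is that the plan has not chosen a bad estimator; it is silent. A reader might infer that an uncorrected variance is specified. The text does not support that, and every figure above is conditional on the usual default.

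A reader might also infer that the primary-endpoint comparison is compromised. It is not: the 2-month test is Welch or Mann-Whitney, and neither uses the GEE variance.

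Three further inferences go too far:
- **Weights.** They do not enter every model. They belong to one of two missing-data approaches compared for robustness.
- **Strict thresholds.** The error is not largest there in absolute terms. Only the ratio grows.
- **FDR.** It cannot be said outright to fail. The SAP does not say whether its family holds GEE p-values, Welch or Mann-Whitney p-values, or both. Under Benjamini-Hochberg only the early steps are very strict, and the realised-FDR figures assume the global null.

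It is also fair that intention-to-treat on 80 enrolled, with GEE keeping partially followed participants, points to the milder part of the range. A check at N=80 gave 5.7 to 6.7% at nominal 5% and 0.53 to 0.70% at 0.38%.

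These points limit the concern without removing it. The direction was the same in every setting run, and the GEE is the source of the adjusted effect.

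**Conclusion.** The concern holds as a conditional and modest one. If the GEEs are run in their usual form, unweighted standard errors would be about 1 to 6% too small and type I error about 5.7 to 7.3% at nominal 5%. The shortfall reaches about 8% in the weighted missing-data analysis with 8 covariates. At nominal 0.38% the error is about 0.5 to 0.75%, so the FDR can exceed its nominal level if GEE p-values enter it.

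The size depends on the number of covariates and the FDR family, neither of which is stated, and on the assumed 1:1 allocation and correlation of 0.5. This is a cheap improvement to the adjusted analyses, not a flaw that undermines the trial.

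**What to change.** Add one sentence to the SAP: all GEE tests and confidence intervals, weighted or not, use a Kauermann-Carroll bias-corrected robust variance with t critical values on the number of participants minus the number of participant-level parameters. With 64 participants, an intercept, group and 5 covariates, that is 64 − 7 = 57 degrees of freedom. The FDR simulation subtracted all 11 mean-model parameters (53 degrees of freedom). The two-sided 5% critical values are 2.002 and 2.006, so the choice hardly matters.

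Mancl-DeRouen with t is a valid alternative but conservative here. The same edit should list the covariates and state the working correlation and the FDR procedure, level and family, since the size of the problem depends on them.

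The cost is one software option and slightly wider intervals. No change to design, sample size or data collection is needed.

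### Diary sleep period time is really the bed-to-wake interval, so it does not register shorter sleep latency or less night waking on their own

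*Combined protocol and SAP*

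**What the plan says.** **Definition.** The Statistical Analysis Plan (sleep paragraph) states: "Sleep period time (SPT) will be calculated from the paper sleep diaries (PSDs) by subtracting self-reported bedtime from wake time".

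**What the diary holds.** Under Procedures, Group A participants are asked to "record what time they went to bed & woke up in a sleep diary" in three separate weeks, and Group B follows the same process. No sleep-onset time, latency or time awake in the night is described.

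**Other sleep information.** The same SAP paragraph derives estimated total sleep time (TST) and sleep efficiency (SE) from Fitbit clock times and sleep and awake minutes. Procedures also has a nightly figure for hours slept entered in Qualtrics, without saying clearly whether it comes from the diary or the device. At all four assessments participants complete the WIS, which asks them to "rate what percent of time worry interfered with their ability to get to or stay asleep", and the PROMIS set, "5 questions taken from the PROMIS v1.0 Sleep Disturbance questionnaire which focus on the interaction between worry and sleep".

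**Analysis.** After defining the sleep variables the SAP says: "Analysis will utilize the same approach as described for the behavioral measures with the addition of a complete case (CC) approach". For the behavioral measures it says: "To examine between-group differences in behavioral outcome measures at the primary endpoint (2 months), Welch's t-tests will be used", followed by GEE models and a false discovery rate correction. The natural reading is that the diary variable is tested in the same way. No sleep variable is named as primary.

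**The concern.** The trial enrols people with a WIS score of at least 5 out of 10, that is, people whose worry keeps them from falling or staying asleep. A sleep-period variable should start when sleep starts. This one starts when the participant goes to bed, so the wakefulness that the intervention is meant to reduce is counted inside it. If that wakefulness turns into sleep and the clock times stay put, the variable does not move.

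At stake is the interpretation of one tested outcome. A flat result could be taken as absence of benefit on diary sleep, and a shift in either direction could be taken as more or less sleep, when it shows only that people changed when they went to bed or woke. The diary as described has no field from which to correct this afterwards.

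**Working it through.** The documents give no effect size, SD, alpha or power for any sleep measure, so there is no stated figure to reproduce. The core of the check is algebra.

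**Notation.** B = bedtime, W = final wake time (both in the diary); L = minutes to fall asleep, N = minutes awake during the night (neither in the diary).

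- Planned SPT = W − B
- Onset-to-wake time = W − (B + L)
- TST = W − B − L − N

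Writing Δ for change:

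- Δ(planned SPT) = ΔW − ΔB
- Δ(onset-to-wake) = ΔW − ΔB − ΔL
- Δ(TST) = ΔW − ΔB − ΔL − ΔN

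L and N do not enter the first line.

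**Step 1: clock times fixed (assumed night).** B = 23:00, W = 07:00, N = 30 min.

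| | L = 60 | L = 15 | Change |
|---|---|---|---|
| Planned SPT | 480 | 480 | 0 |
| Onset-to-wake | 480 − 60 = 420 | 480 − 15 = 465 | +45 |
| TST | 420 − 30 = 390 | 465 − 30 = 435 | +45 |
| TST / (W − B) | 390/480 = 81.25% | 435/480 = 90.6% | +9.4 points |

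**Step 2: clock times move as well.** Latency falls by 30 min (ΔL = −30), and the bed-to-wake interval also changes.

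| Change in W − B | Planned SPT | Onset-to-wake | Reading |
|---|---|---|---|
| 0 | 0 | +30 | null, true gain |
| −15 (half the gain given up) | −15 | +15 | wrong direction |
| −30 (all given up) | −30 | 0 | apparent loss, no true change |
| +15 | +15 | +45 | partial gain |

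**Step 3: illustration of power.** Assumptions: the 64 complete data sets (Participant enrollment target) split 32 per arm, two-sided alpha 0.05, and no group difference in clock times. SE = SD × √(2/32) = SD/4, and power ≈ Φ(gain/SE − 1.96). For example, SD 45 and gain 30 give SE = 11.25, 30/11.25 = 2.67, Φ(0.71) = 0.76.

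Power for onset-to-wake time:

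| SD (min) | Gain 15 | Gain 30 | Gain 45 |
|---|---|---|---|
| 45 | 0.27 | 0.76 | 0.98 |
| 60 | 0.17 | 0.52 | 0.85 |
| 75 | 0.12 | 0.36 | 0.67 |

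For planned SPT the expected difference is 0 in every cell, so the rejection rate is 0.05, the type I error.

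**Step 4: a second assumed set.** In 5,000 simulated trials at 32 per arm with Welch's test, latency is 20 min shorter, night waking is 10 min less and clock times are unchanged. The assumed SDs are 50 min each for bed and rise times, 30 for latency and 25 for night waking. Rejection rates were 4.6% for planned SPT, 18.7% for onset-to-wake time, 31.3% for diary TST and 75.5% for diary latency. Scatter in the two clock times alone gives √(50² + 50²) = 70.7 min. Both onset-to-wake time and TST carry that scatter; latency does not.

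**The case against.** The other side has several good points.

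- **A reader might infer that the variable cannot change, or that its effect is zero by construction.** That is too strong. The zero in Steps 1, 3 and 4 depends on bed and wake times staying fixed. If worry causes early final waking and treatment delays that waking by 30 min, planned SPT and onset-to-wake time both rise by 30. The variable is blind to latency and mid-night waking, not to every part of the target.
- **A reader might infer that the trial will conclude there is no sleep effect.** The documents do not support this. Nothing says a sleep benefit will be judged on the diary variable, and Fitbit TST and SE, the WIS, the PROMIS items and the hours-slept figure are also collected. The WIS and PROMIS items are tied to worry, but worry-related sleep difficulty is what this trial targets, so that does not disqualify them.
- **A reader might infer that the Fitbit cannot make up for a missing latency item.** The documents do not settle this. No device latency variable is planned, but whether the Fitbit's bedtime or awake minutes include wakefulness before sleep cannot be judged from the text.
- **A reader might infer that the variable wastes a test under the false discovery rate correction.** The SAP does not define the family, so this cannot be shown.
- **The power figures rest on assumptions, and redefinition alone may not help much.** This stands. In Step 4 the corrected SPT reaches only about 19%.

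What survives is narrower: the label does not match the formula, the formula misses two of the main routes by which sleep could improve, and the diary cannot repair it.

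**Conclusion.** The point holds for the diary outcome. As defined, it is the bed-to-wake interval, and it does not respond to a fall in latency or night waking alone. *Time in bed* would also be inexact, because the interval ends at waking and not at getting up.

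The algebra needs no assumptions. The size of the miss equals the change in latency for onset-to-wake time (45 min in the worked night), and the change in latency plus night waking for TST. When clock times shift too, the result can be null, partial or reversed, and the planned diary cannot tell these apart. The power range for onset-to-wake time, about 0.12 to 0.98, is illustrative and depends on the assumed 32 per arm, gains of 15 to 45 min and SDs of 45 to 75 min.

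This is an inexpensive improvement to one outcome. It does not undermine the trial's sleep conclusion as a whole, because the device and questionnaire measures remain.

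**What to change.** 1. Add two entries per night to the paper diary: minutes taken to fall asleep, and minutes awake during the night.
2. In the SAP, define diary latency from the first entry, SPT as wake time minus (bedtime + latency), and diary TST as that SPT minus the second entry.
3. Rename the present variable *bed-to-wake interval*, and state that it will not be interpreted as evidence for or against a sleep benefit.
4. If the diary cannot be changed, apply item 3 and rely on the already planned Fitbit TST and SE for sleep duration and efficiency.

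The cost is 2 entries × 7 nights × 3 weeks = 42 extra numbers per participant, and one revised SAP definition. The downsides are slightly more burden and estimation error in self-reported latency. Item 3 adds no data collection and is worth adopting in either case. Which diary variable should lead is for the sponsor to decide; this point does not depend on it.
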